With recent work highlighting that peanut introduction in early infancy can protect against peanut allergy development in childhood^{6,7}, there has been a shift in recommendations for complementary feeding practices. Contrary to traditional recommendations (ESPAI, 1999⁸ and AAP, 2000⁵), recent national (AAP, 2019)⁹ and international (EAACI, 2014)¹⁰ guidelines report that there is no evidence to suggest that withholding the introduction of allergenic foods to infants after 4-6 months is protective against allergy development. However, compared with peanuts, the ideal age for egg introduction into the infant diet is still debated (AAP, 2019)⁹. Egg allergy is often perceived as one of the most common food allergies in early childhood by health professionals and parents, contributing to a major consumer perception obstacle for the egg industry and a potential barrier to widespread egg infant consumption^{10,11}. In support of current recommendations, more recent work has reported either no influence¹² or even a protective effect¹³ of egg introduction at 4-6 months of age on allergy risk in infants older than 12 months. A recent systematic review and meta-analysis of 146 interventional and observational studies of timing of allergenic food introduction concluded that there was moderate-certainty evidence to support early egg introduction at 4-6 months to reduce egg allergy (risk ratio [RR], 0.56; 95% CI, 0.36-0.87; p=0.009)¹⁴. Five of the 6 studies reported a protective effect of early egg introduction on egg allergy (RR point estimate, 0.22-0.69). In the outlier study, Bellach et al. reported that infants randomized to egg white powder had a doubled risk of egg sensitization at 1 year of age versus those in the control rice powder group (5.6% versus 2.6%; RR 2.20; 95% CI, 0.68-7.14), however these results did not reach statistical significance (p=0.24)¹⁵.

An optimal infant egg introduction strategy must consider multiple childhood and food-influencing factors, including both age of egg introduction, frequency (amount) of egg consumption, and egg fraction¹⁴. Tran et al.¹⁶ recently investigated how early (0-6 months), usual (7-12 months), and delayed (avoidance during first year) timing of egg introduction influenced food sensitization. They reported that introduction of eggs at 0-6 months versus 7-12 months was associated with no increased risk of egg allergy at 1 year of age; further, total

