DHA (22:5n-3), an essential long-chain fatty acid found in conventional and omega-3 enriched eggs, is critical for early fetal growth and the development of neurological function³². Pregnant and nursing women are advised to consume at least 200 mg of DHA daily; however, dietary intake is below recommendations in the majority of US women during pregnancy³³. Previous work has reported that children from mothers supplemented with DHA from delivery until 4 months have better sustained attention at 5 months of age³² and improved psychomotor development measured at 2.5 years of age³⁴. Further, maternal supplementation of choline, another egg-rich nutrient has been associated with protection against cognitive impairment due to prenatal alcohol exposure³⁵. However, although a recent prospective cohort study reported that egg consumption was associated with enhanced cognitive performance in adults³⁶, the impact of infant egg consumption on cognitive performance during childhood is not known.

Summary of Current Knowledge and Research Priorities:

- Allergy concerns have traditionally led to slow introduction practices or complete avoidance of eggs during the first year of life, despite the high nutrient value of eggs.
- Although recent research supports early infant egg exposure to reduce childhood egg allergy, optimal egg introduction strategies (age, frequency/amount, fraction) are still debated among parents and healthcare professions, creating a barrier for widespread infant egg consumption.
- Optimal infant egg consumption guidelines must balance allergy concerns with broader assessments of child health and development, including physical growth, obesity, cardio-metabolic health, and cognitive development.
- Currently, there is insufficient knowledge of how the age of infant egg introduction and frequency of egg intake influence whole-body child health and development.

2) Research Project Objectives and Hypotheses:

[figure not shown]
Objectives: To examine the longitudinal associations of infant age of egg introduction (**Aim 1**) and frequency of infant egg intake (**Aim 2**) with physical growth, obesity, cardio-metabolic health, risk of food allergy, and cognition development in mid-childhood and adolescence.

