Hypotheses: The effects of infant age of egg introduction and frequency of egg intake will vary by the child outcome of interest (**Hypothesis 1**). We predict a non-linear association between age of egg introduction and the average probability of multiple child outcomes (i.e., stunting, underweight, obesity, high risk of metabolic syndrome, food allergy, and cognitive delay), with the optimal age being a time point that falls between 6-12 months (**Hypothesis 2**). We also predict a non-linear association between frequency of infant egg intake and the average probability of multiple child outcomes, with the optimal frequency being 2-4 times per week (**Hypothesis 3**).

3) Project Design:

Sample/Data. We propose a 2-year study to examine the extent to which two important aspects of infant egg consumption (i.e., age of introduction and frequency of intake) influence physical growth, obesity, cardio-metabolic health, risk of food allergy, and cognition development in mid-childhood and adolescence. Guided by a life course framework (**Figure 1**), we will use existing secondary data from two US longitudinal birth cohorts that tracked mother-child dyads from pregnancy to adolescence: 1) **Project Viva** (1999-present, N=2,128 newborns) that followed children at delivery, 6 months (m), 1 year (y), 2 y, 3 y, 4 y, 5 y, 6 y, 7 y, 8 y, 9 y, 10 y, 11 y, 12-13 y, 14 y, and 15 y of child age,³⁷ and 2) **Infant Feeding Practices Study II** (IFPS II, 2005-2012, N=3,033 newborns) that followed children at neonatal (1 m), 2 m, 3 m, 4 m, 5 m, 6 m, 7 m, 9 m, 10 m, 12 m, and 6 y of child age.^{38,39} The PI has access to both datasets, and has 3 publications on infant nutrition, early childhood diet, growth, and obesity using Project Viva^{40,41} and IFPS II⁴² data since 2014. These two studies have a similar study design and complementary measures of child outcomes, which provide a unique opportunity for comprehensive analysis on the health effects of infant egg consumption and also external replication of findings.

Exposure measures (infant egg consumption). We will focus on age of introduction and frequency of intake as the key exposure measures of infant egg consumption, because evidence

Infant Egg Consumption | Child Health and Cognition | Clinical Guidelines

Figure 1. Conceptual framework on effects of infant egg consumption

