supports their potential influences on child health and development⁴³. We recognize that other aspects of infant egg consumption such as different egg fractions (i.e., white vs yolk⁴⁴) may also influence child outcomes but they were not collected in Project Viva or IFPS II.

Age of egg introduction. At **Project Viva** visits, the age of infant egg introduction was asked at 6-m and 12-m using the same question - “How old was your baby when you first fed him/her eggs”. In the **IFPS II**, mothers reported their infant’s intake of 18 types of foods in the past 7 days through monthly surveys from 2-12 m of infant ages. The question used for infant food intake was - “In the past 7 days, how often was your baby fed each food listed below? Include feedings by everyone who feeds the baby and include snacks and night-time feedings.” “Eggs” were one of the 18 types of foods. Accordingly, we will derive the infant age of egg introduction from IFPS II mothers’ monthly responses to infant egg consumption. Our previous analysis on infant dietary patterns showed that 1.7% and 63.0% of IFPS II infants had been introduced eggs by 6 m and 12 m of age, respectively⁴².

Frequency of egg intake. At the 2-y survey in **Project Viva**, the frequency of infant egg intake in the past month was obtained from the mothers’ response to the question - “Please check the box that best represents how often your child eats each of the foods listed, on average, in the past month”. One of the food items for this question was “Whole eggs”. Response options for the frequency of consuming “Whole eggs” included “never”, “<once/week”, “once/week”, “2–4 times/week”, “nearly daily or daily”, and “≥2 times/day”.

The same question was asked again at surveys at 3 y and 7 y. As mentioned above, mothers in the IFPS II reported their infant's intake of eggs in the past 7 days through the monthly surveys from 2-12 m of infant ages. Infant egg intake was reported as the number of feedings per day or per week. Our analysis on infant dietary patterns showed the mean egg intake among IFPS II infants was 0.01 (SD, 0.10) and 0.27 (SD, 0.37) serving/week at 6 m and 12 m, respectively⁴².

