Cardio-metabolic health. At the 7-y and 12-13-y visits in Project Viva, the child's systolic (SBP) and diastolic blood pressure (DBP) were measured with automated oscillometric monitors. In addition, the child's fasting blood was used to measure plasma glucose, insulin, adiponectin, and C-reactive protein (CRP), serum total cholesterol (TC), triglycerides (TG), and HDL⁴⁸. We will calculate LDL as, total cholesterol – HDL – (triglycerides/5). We will estimate insulin resistance through the homeostatic model assessment of insulin resistance (HOMA-IR = [glucose mg/dL \times insulin μ IU/mL]/405). A metabolic syndrome z score was derived by calculating the mean of five age- and sex-specific internal z scores for waist circumference, SBP, inverted HDL, natural log-transformed TG, and natural log-transformed HOMA-IR⁴⁸.

Risk of food allergy. In Project Viva, mothers reported the child's food allergy annually from 2 y to 11 y, at 12-13-y and 14-15-y of child age through the questions, - "In the past month, has your child avoided any foods because of a food allergy, intolerance, or sensitivity?", and "If yes, please specify". More details on food allergy were reported at the 7-y and 12-13-y visits using the question, - "Has your child ever had an allergic reaction to fish, shellfish, sesame seeds, peanuts or tree nuts?". In addition, at the 7-y and 12-13-y visits, food allergen sensitization of the child was defined as any serum specific IgE level of 0.35 IU/mL or greater to one of the food allergens listed, i.e., egg white, milk, wheat, peanut, and soybean⁴⁹. In the IFPS II, mothers reported whether their infant had food allergy in the past 2 weeks at 2-12 m of infant ages. Additional information on infant food allergy was collected at 4, 9, and 12 m:

whether food allergy (e.g., allergic reaction, sensitivity, or intolerance) happened at the first time of eating, exposure pathway, initial age, allergic symptoms, doctor visit, methods for testing food allergy, diagnosis, treatments, and food allergens including eggs. At the 6-y follow-up, mothers reported the child's status and history of food allergy, initial age, symptoms, testing methods, diagnosis, treatments, outgrowing food allergy, and food avoidance.

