Cognition development. In Project Viva, the child's cognition development, including intelligence, visual-motor, and memory-learning, was measured at 3 y and 7 y of age⁵⁰. For the intelligence domain, trained research staff administered the Peabody Picture Vocabulary Test-3rd edition (PPVT-III, a test of receptive language) at 3 y of age, and the Kaufman Brief Intelligence Test-2nd edition (KBIT-II, verbal and non-verbal intelligence) at 7 y of age. For the visual-motor domain, research staff administered the Wide Range Assessment of Visual Motor Abilities (WRAVMA) at the 3-y visit. WRAVMA includes the fine motor (pegboard), visual spatial (matching), and visual motor (drawing) subtests. Subtest scores were combined to yield the total WRAVMA score. At the 7-y visit, staff administered the WRAVMA visual motor (drawing) subtest only. For the memory-learning domain, staff administered the design memory and picture memory subsets of Wide Range Assessment of Memory and Learning (WRAML) at the 7-y visit. These two subset scores were combined to yield the total WRAML score.

Effect modifier. We are interested in effect modification by child sex (Boys vs Girls).

Confounders. Potential confounders include family income; health history of family members; parental education attainment, employment, and preconception BMI; and maternal intelligence, age, race/ethnicity, marital status, parity, pregnancy complications, prenatal vitamins, smoking, and delivery method; early mode of infant feeding including breastfeeding duration and exclusivity. We will also adjust for child actual age at assessments.

Data analysis. All our analyses will be first conducted among boys and girls separately to examine the potential sex differences (if significant, sex-stratified results will be reported).

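### The food-allergy analyses do not separate low or late egg intake from egg stopped or withheld because of an earlier infant allergy; a separate, minor point is that only undefined significant covariates are kept

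*Combined protocol and SAP*

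**What the plan says.** **Covariates.** Under Project Design, Confounders, the list begins "Potential confounders include family income; health history of family members; parental education attainment, employment, and preconception BMI". It continues with maternal and pregnancy factors and ends with mode of infant feeding. Family health history is the only item that could carry allergic tendency. Child age at assessment is the only covariate adjusted for without condition. Data analysis then adjusts the regression and mixed models only for confounders or covariates that are significant. The missing-data paragraph names only significant covariates among the variables to be imputed. No test or threshold is given.

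**Exposure.** For Aim 2 in Project Viva, "the frequency of infant egg intake in the past month was obtained from" the mothers at the 2-y survey. In IFPS II, both egg age and egg frequency come from the item "In the past 7 days, how often was your baby fed each food listed below".

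**Allergy data.** From 2 y, Viva mothers are asked each year "In the past month, has your child avoided any foods because of a food allergy, intolerance, or sensitivity". Viva also has food-specific IgE at 7 y and 12-13 y. IFPS II has food-allergy reports at 2-12 m, with initial age and egg as a possible allergen at 4, 9 and 12 m, and a 6-y follow-up. All of this is described under outcomes. None of it is used to establish whether allergy or egg exposure came first.

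**Use.** Outcomes are compared in mid-childhood and adolescence. Food allergy is one of six equally weighted outcomes in the average that picks the lowest-risk egg age or frequency.

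**The concern.** The plan's own summary gives the mechanism: "Allergy concerns have traditionally led to slow introduction practices or complete avoidance of eggs during the first year of life". If an infant allergy leads a family to stop or withhold egg, and the allergy persists into the outcome window, the allergy has caused the exposure. Measuring the outcome years later does not remove this.

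- **Aim 2** is the clearest case. Egg may be stopped after a reaction. In Viva, intake is recorded at the same survey age at which avoidance for allergy is first asked.
- **Aim 1** is weaker, because a reaction to egg cannot precede first egg. What remains is earlier allergy to another food, allergy concern (partly covered by family history) and, in IFPS II only, a brief feeding that 7-day recall misses, so that an infant who was fed, reacted and stopped is coded late or never.

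The bias runs one way: low or late egg looks worse for allergy. That is the direction the background leads readers to expect, citing early introduction "to reduce egg allergy (risk ratio [RR], 0.56; 95% CI, 0.36-0.87; p=0.009". It can exaggerate a real benefit or mask a real harm, and it adds a gradient to the six-outcome average.

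**Working it through.** **1. The plan's figure, for scale.** Statistical Power gives detectable odds ratios of 1.46 (N=2,128) and 1.38 (N=3,033) without a baseline risk or group split. Assuming 10% baseline risk, the whole cohort split 1:1 and a two-sided 5% test, 80% power gives 1.458 and 1.376. The point does not depend on these.

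**2. Spurious odds ratio under no egg effect.** Let u be the share of children in the unfed or lowest-intake group. Let q be the share of later-allergic children placed there by their allergy. Everyone else is distributed as the cohort is. Then

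OR = [q + (1−q)u] / [(1−q)u] = 1 + q / [(1−q)u].

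The composite shift is one sixth of the allergy risk difference, with 8% risk in the reference group (assumed).

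| Setting | u | q (assumed) | OR | Shift in average (points) |
|---|---|---|---|---|
| Viva, Aim 2 | 0.10 (assumed) | 0.05 | 1 + 0.05/0.095 = 1.53 | 0.62 |
| Viva, Aim 2 | 0.20 (assumed) | 0.05 | 1 + 0.05/0.19 = 1.26 | 0.32 |
| Viva, Aim 2 | 0.50 (assumed) | 0.05 | 1 + 0.05/0.475 = 1.11 | 0.13 |
| IFPS II, Aim 1 | 0.37 | 0.01 | 1.03 | 0.03 |
| IFPS II, Aim 1 | 0.37 | 0.05 | 1.14 | 0.17 |
| IFPS II, Aim 1 | 0.37 | 0.10 | 1.30 | 0.36 |
| IFPS II, Aim 1 | 0.37 | 0.20 | 1.68 | 0.79 |

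Example of the shift (first row): odds 0.08/0.92 × 1.526 = 0.1327, risk 0.1172, and (0.1172 − 0.08)/6 = 0.0062.

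The documents do not give Viva's lowest-intake share at 2 y. The 0.37 is 1 − 0.63, from "1.7% and 63.0% of IFPS II infants had been introduced eggs by 6 m and 12 m of age, respectively". Metabolic and cognitive outcomes are described only for Viva, so the Viva rows are the ones relevant to the average.

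**3. Missed brief feedings, IFPS II only.** A single feeding on a random day falls outside a 7-day window in a 1-month gap with probability 1 − 7/30.4 = 0.77. This assumes egg was fed exactly once.

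**4. Do restricted analyses help?** Simulation of not fed by 12 m versus fed at 6-12 m, using the IFPS II introduction shares. Assumed: allergy onset in 4% over 2-12 m and in 4% later, and egg withheld in a given share of infants whose allergy came first.

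| True egg effect | Withheld | Unrestricted OR | 6-m landmark | 12-m landmark |
|---|---|---|---|---|
| None | 14 / 29 / 57% | 1.14 / 1.32 / 1.69 | 1.07 / 1.16 / 1.33 | 1.00 throughout |
| Protective, RR 0.56 | 0 / 29 / 57% | 1.42 / 1.94 / 2.65 | 1.58 / 1.87 / 2.23 | 1.80 / 1.79 / 1.80 |
| Harmful, RR 1.8 (assumed) | 0 / 29 / 57% | 0.64 / 0.82 / 1.00 | 0.59 / 0.67 / 0.75 | 0.54 / 0.55 / 0.54 |

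The 6-m landmark removes part of the bias and the 12-m landmark removes it in these settings. If the egg effect acts only in the first year, the 12-m landmark returns 0.99-1.00 and cannot see it. With strong assumed frailty, selection alone moved it to 0.98-1.04.

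**5. Selecting covariates on significance.** Simulation with an 8% outcome, N=2,128, no egg effect and 16 weak confounders (assumed).

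| Confounder directions | Rule | Coverage of 95% CI |
|---|---|---|
| All one way | p<0.05 with outcome | 63-90% |
| All one way | p<0.20 with outcome | 91-95% |
| All one way | p<0.05 with exposure | 94-96% |
| All one way | full list | 94-95% |
| Mixed | p<0.05 with outcome | 93-97% |

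With a 50:50 binary exposure, confounders all one way and the p<0.05 outcome rule, coverage was 91-93%.

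**The case against.** The list is introduced as potential confounders that are included, so it need not be exhaustive, and family history covers some allergy concern. Both are fair. But family history is not the child's own allergy and may be dropped as non-significant, and nothing in Data analysis puts allergy and exposure in time order.

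Every rate behind the odds ratios is assumed. That stands: they show what the plan permits, not what it will produce.

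Four stronger readings are tempting, and the documents do not support them.

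- **That Viva Aim 1 cannot be protected.** Viva asks about avoidance from 2 y, so the 2-y exclusion available for Aim 2 can be applied to Aim 1, with the same selection limit. Viva also asks directly for age at first egg, so the recall route does not arise there.
- **That the 37% rows measure the main problem.** They describe IFPS II Aim 1, whereas the route is strongest in Aim 2 and the average is Viva-based.
- **That 89% of single feedings are missed (1 − 7/60.9).** This needs a 2-month gap. Sample/Data lists "6 m, 7 m, 9 m, 10 m, 12 m, and 6 y of child age", without 8 m or 11 m, but the opening summary and the exposure section describe monthly surveys.
- **That significance-based selection generally ruins coverage.** The marked loss appeared only with selection on the outcome at p<0.05 and confounders all running one way. The missing-data paragraph also says which variables are imputed. That the imputation models contain nothing else is an inference.

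**Conclusion.** (a) The concern holds. As written, the food-allergy models can return a gradient against low or late egg when egg has no effect, and that gradient enters the six-outcome average. It is clearest in Aim 2 and weaker in Aim 1. The size is not computable from the documents. At q = 5%, the illustrative odds ratio is 1.11 to 1.53 for lowest-intake shares of 50% down to 10%, all assumed. A reader might infer that the lowest-risk age or frequency will move. That depends on the other five outcomes, which cannot be computed from the documents.

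(b) This is separate and minor. Keeping only significant covariates, undefined, can leave residual confounding when confounders run the same way and selection is on the outcome. It does little harm when directions are mixed.

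The change is worth making because it is cheap and uses data already held.

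**What to change.** **1. Food-allergy sensitivity analyses, reported beside the unrestricted results.**
- IFPS II, both aims: exclude infants with food allergy reported before 6 m, classify egg exposure after that, and use the 6-y outcome. Repeat with one 12-m landmark for every group, never-fed included, counting only allergy that began later.
- Viva, both aims: exclude children already avoiding foods for allergy at the 2-y survey, count only mid-childhood and adolescent outcomes, and show IgE sensitization separately from the avoidance item.
- Report the six-outcome average with and without food allergy, and with the Viva 2-y exclusion.
- State the limits. The 6-m landmark removes only part of the bias. The 12-m landmark and the 2-y exclusion condition on allergy that may follow egg, so they cannot show an earlier effect and may be subject to selection.

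**2. Covariates.** Replace the significance condition with a set fixed in advance from the Confounders list, limited to what each cohort measured and used in both outcome and imputation models. For rare outcomes in sex-specific models, name a smaller fixed set or penalised logistic regression.

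**Cost.** Plan wording, a few extra models and wider intervals. If 4% have onset by 12 m and 4% later, all still counted at 6 y (assumed), IFPS II has 0.08 × 3,033 ≈ 243 events before attrition. The 6-m landmark leaves 0.064 × 3,033 ≈ 194 and the 12-m landmark 0.04 × 3,033 ≈ 121. With SE ≈ 1/√[n p(1−p) u(1−u)] and u = 0.37, where n is the number of children left and p the risk among them, the SE of the log odds ratio rises from 0.139 to 0.154 (11% wider) and 0.192 (39% wider).

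Full adjustment also has a price. If stunting follows the normal share below −2 (assumed), Viva has 0.02275 × 2,128 ≈ 48 events, or 24 per sex. In simulation, 16 covariates then gave a diverging estimate in about 15% of sex-specific fits, against 0% with 5 covariates or a Firth fit.

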Child outcome measures. We will focus on child physical growth, obesity, cardio-metabolic health, risk of food allergy, and cognition development (**Figure 1**). These child outcomes were chosen because they 1) may be influenced by infant egg consumption (see '**Background**'), 2) are clinically important, and 3) were measured in Project Viva and/or IFPS II.

Physical growth. In Project Viva, birth weight was obtained from birth certificates. Research staff measured children's length/height, weight, and waist circumference at 6 m (infancy), 3 y (early childhood), 7 y (mid-childhood), 12-13 y (early teen), and 14-15 (mid-teen)^{37,45}. Additional data on child weight and length/height were obtained from medical records at well-child visits. In IFPS II, mothers reported infant birth weight and length in neonatal survey; weight, length, and age at their most recent doctor's visit in 3-m, 5-m, and 7-m, 12-m, and 6-y surveys^{38,42}. Body mass index (BMI) was calculated as, weight in kg/(height in meters)². We will define stunting as height-for-age z score < -2, and underweight as sex- and age-specific BMI < 5th percentile according to World Health Organization (WHO) Growth Standards^{46,47}.

Obesity. In both Project Viva and IFPS II, we will define child obesity as sex- and age-specific BMI \geq 95th percentile according to WHO Growth Standards^{46,47}. In Project Viva, skinfold thickness was measured at 3 y, 7 y, 12-13 y, and 14-15 y. In addition, fat, lean and trunk fat mass were measured through whole-body dual X-ray absorptiometry (DXA) scans performed at 7 y, 12-13 y, and 14-15 y. Accordingly, we will calculate fat mass index (FMI, kg/m²), lean mass index (LMI, kg/m²), and trunk fat mass index (TFMI, kg/m²).

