For **Aim 1 (infant age of egg introduction)**, we will first classify the infants based on their age of egg introduction: never, <2 m, 2-3 m, 4-5 m, 6-8 m, 9-11 m, and 12 m. Then we will compare their physical growth, obesity, cardio-metabolic risk profile, risk of food allergy, and cognition test scores in mid-childhood and adolescence using Chi-square tests (categorical outcomes) or ANOVA tests (continuous outcomes). We will fit multivariable linear (continuous outcomes) or logistic (binary outcomes) regression models with fractional polynomial functions of infant age of egg introduction, adjusted for significant confounders. Both linear (e.g., earlier introduction, high probability of the outcome) and non-linear (e.g., threshold effect) associations will be tested. The non-linear trend will be examined through visualization of scatter plots and statistical tests of polynomial term of infant age of egg introduction in the regression models. If the polynomial terms of age are not significant, we will drop it and consider the association to be linear.

Then, we will fit a mixed effect model (SAS PROC MIXED) for continuous outcomes (height z-score and BMI z-score) and a generalized linear mixed effect model (SAS PROC GLIMMIX) for binary outcomes (obesity and diagnosis of food allergy) that were measured repeatedly across multiple age points. The mixed effect model will include random intercepts, random slopes for age effects, and autoregressive variance-covariance matrix across different time points. Independent variables in the model will include infant age of egg introduction, outcome age point (mid-childhood and adolescence), the 2-way interaction term (infant age of

egg introduction × outcome age point), and significant covariates. The 2-way interaction term quantifies the extent to which infant age of egg introduction can affect the specific outcome. The PI has experience with using mixed effect models for examine child growth measures and multiple publications in this area.^{51,52}

For **Aim 2 (frequency of infant egg intake)**, we will first classify the infants based on their frequency of egg intake: never, <once/week, once/week, 2–4 times/week, nearly daily or daily, and ≥ 2 times/day. Then, we will use similar analytic methods mentioned above for Aim 1 to compare their health and developmental outcomes.

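### Birth weight is held in both cohorts but is not a named covariate, which risks residual confounding of growth and obesity results and gives up modest precision for continuous outcomes

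*Combined protocol and SAP*

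**What the plan says.** The Confounders paragraph opens with "Potential confounders include family income; health history of family members; parental education attainment, employment, and preconception BMI", goes on to maternal, pregnancy and delivery factors, and ends with "early mode of infant feeding including breastfeeding duration and exclusivity". The only child-level covariate it adds is age: "We will also adjust for child actual age at assessments". Child sex is handled separately as an effect modifier. Birth size, early infant size and the timing of other foods are not named.

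The Data analysis section (Aim 1) says the models will be "adjusted for significant confounders". It does not say what counts as significant, or whether that is judged per outcome or per cohort.

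The data exist. Under Physical growth: "In Project Viva, birth weight was obtained from birth certificates", and for IFPS II, "mothers reported infant birth weight and length in neonatal survey". The same paragraph gives measured size at 6 m in Project Viva, and mother-reported weight, length and age at the latest doctor's visit in the 3-m and 5-m surveys of IFPS II. Under Age of egg introduction, IFPS II recorded each infant's "intake of 18 types of foods in the past 7 days through monthly surveys". For Project Viva that paragraph describes only the egg question.

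**The concern.** Later height, BMI, stunting, underweight and obesity are outcomes here. A child's size at birth comes before any egg feeding, plausibly influences when solids are offered, and is likely to predict later size. A variable with those properties belongs in the adjustment set. An open-ended list combined with a significance rule does not ensure that it gets there, and it could be dropped from one model and kept in another.

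Any bias would carry forward. Stunting, underweight and obesity are three of the six equally weighted outcomes in the average probability that selects the lowest-risk egg age or frequency. A fourth, the metabolic syndrome score, includes waist circumference.

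The timing of other solids raises a related question. The Background itself says that the timing of food introduction in general affects child health, and that infants who eat eggs have a different accompanying diet. Without some account of when other solids began, an association with egg age may partly reflect early or late complementary feeding as a whole.

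**Working it through.** **The plan's own figures.** The plan gives no figure for the adjustment set. The nearest scale is the detectable effect for continuous outcomes under Statistical Power: 0.054 (Project Viva, N = 2,128) and 0.051 (IFPS II, N = 3,033), at type 1 error 0.05 and power 0.8. Its metric is not stated. Reading it as a correlation-type effect, (z for alpha + z for power)/√N:

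- IFPS II, two-sided: (1.960 + 0.842)/√3,033 = 0.051, which matches.
- Project Viva, two-sided: 2.802/√2,128 = 0.061, which does not match. One-sided, (1.645 + 0.842)/√2,128 = 0.054 does.

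The pair does not follow one convention, so I use the two-sided values only as a scale.

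**Precision, continuous outcomes.** For a baseline covariate unrelated to exposure, with correlation r to the outcome, the SE is multiplied by √(1 − r²), equivalent to multiplying N by 1/(1 − r²). The documents give no r; 0.2 to 0.3 for birth weight and later size is an assumption.

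| Assumed r | SE factor | Equivalent N | Detectable effect, Viva | Detectable effect, IFPS II |
|---|---|---|---|---|
| none | 1 | 1 | 0.061 | 0.051 |
| 0.2 | √0.96 = 0.980 | 1.04 | 0.060 | 0.050 |
| 0.3 | √0.91 = 0.954 | 1.10 | 0.058 | 0.049 |

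The gain is an SE about 2 to 5% smaller.

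**Precision, binary outcomes.** Stunting, underweight and obesity go into logistic models, where that formula does not apply. In a simulation (N = 2,128, baseline risk about 10%, egg log-odds 0.18 per SD, birth size independent of exposure, 600 datasets per setting), adding birth size with log-odds 0.2, 0.4 or 0.6 moved the SE of the egg coefficient from 0.0721 to 0.0722, 0.0707 to 0.0713 and 0.0686 to 0.0701. Power changed by about one percentage point. There is no precision gain to claim.

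**Confounding.** Bias in a standardised coefficient is approximately the correlation of exposure with the omitted variable times that variable's standardised effect on the outcome. Neither input is in the documents. If the correlation of birth size with egg age were 0.1 to 0.2 and its effect on later size 0.2 to 0.3, the bias would run from 0.1 × 0.2 = 0.02 to 0.2 × 0.3 = 0.06. That is below to slightly above the detectable effect. It shows only that modest values could matter, and it allows nothing for what the listed covariates already absorb.

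**Which early size is pre-exposure.** The plan reports that 1.7% of IFPS II infants had eggs by 6 m; applied to all 3,033, that is 0.017 × 3,033 ≈ 52 infants. Size from the 3-m or 5-m survey therefore precedes egg exposure for at least 98.3%. No such figure is given for Project Viva, and its 6-m size may follow exposure in infants given eggs earlier.

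**Cost of adjusting for solids timing.** If egg age correlates with age at first other solid at an assumed 0.3 to 0.5, the SE is multiplied by 1/√(1 − 0.09) = 1.05 to 1/√(1 − 0.25) = 1.15.

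**The case against.** The list is introduced as potential confounders, so birth weight is not excluded. Several named items, such as preconception BMI, smoking, parity and pregnancy complications, are plausible determinants of birth size and may already absorb part of the confounding. The infant-feeding item could be read to include solids. Adjusting for infant size also risks conditioning on a consequence of egg feeding.

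Some of this stands. How much confounding remains after the listed covariates is unknown, and later infant size could lie on the causal path. But an open list does not commit the analyst to birth weight, and the significance rule could remove it even if it were considered. The only feeding examples given concern breastfeeding. The causal-path point cannot apply to birth size and barely applies to 3-m or 5-m size in IFPS II.

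A reader might go further and infer that the results are confounded, that every growth and obesity model loses precision, or that both cohorts hold the timing of other solids. The documents do not support these. They contain nothing from which the confounding can be measured. The precision argument fails for the logistic models. Timing of other foods in infancy is described for IFPS II only, and adjusting for it widens the SE. Nor do they support a large precision gain from early-infancy size, since that would rest on an assumed strong correlation with size years later.

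**Conclusion.** The point holds in limited form. Birth weight, a pre-exposure measure held in both cohorts, is absent from the named covariates, and nothing in the plan secures its inclusion. The consequence is a plausible risk of residual confounding in the growth and obesity results, of a size the documents cannot give. There is also a modest loss of precision for continuous outcomes: about 2 to 5% of the SE, if birth weight and later size correlate at 0.2 to 0.3. Separating an egg association from complementary feeding in general can be examined in IFPS II; the documents do not show that it can be in Project Viva. The change is worth making because it is cheap and the variable is already held, not because a bias has been demonstrated.

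**What to change.** - Name birth weight, as a sex-specific z score, as a covariate kept regardless of significance in the growth and obesity models of both cohorts, and in the metabolic and cognition models of Project Viva, the only cohort for which those outcomes are described.
- In the IFPS II growth and adiposity models, add weight and length z scores from one fixed early survey, 3 m or 5 m, computed at the age reported for that doctor's visit. Do not use the last measurement before eggs were introduced: the age of measurement would then depend on the exposure, and infants never given eggs would have no defined value.
- In IFPS II, report a sensitivity analysis that adds age at first non-egg solid food, derived from the food grid, and show results with and without it. State in advance which of the 18 items count as solids, since the document names only eggs.

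The cost is a few covariates from data already held, with missing values handled by the multiple imputation already planned. The solids-adjusted analysis will have a wider SE, by a factor of about 1.05 to 1.15 at an assumed exposure correlation of 0.3 to 0.5, and should be read with that in mind.
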